The current study is designed to compare the effect of high intensity interval training versus moderate continuous training exercise on soluble ST2 biomarker level in chronic heart failure patients with New York heart association (NYHA) classification I, II.

Patients:

This study will be carried out on sixty male patients suffering from chronic Heart failure NYHA classification (I & II) with an age range from 50 to 60 years old. The patients will be selected from Aldmerdash hospital, Ain shams university and patients will be randomly assigned into two groups. The purpose, nature and potential risk of the study will be explained to all patients.

Ethical considerations:

- Approval of faculty ethical committee.
- The study procedures will be explained for all participants.
- Confidentiality will be assured.
- An informed consent will be taken from each subject prior to participation (Appendix I).

Criteria for the patient selection:

Inclusion Criteria:

The patient selection will be according to the following criteria:

- They will have chronic heart failure (New York heart association class I& II) systolic left ventricular dysfunction.
- Their left ventricular ejection fraction (LVEF) <40%.
- Medical treatment will be optimized at least three months prior to study entry.
- All patients didn't participate in any rehabilitation programs prior to the study.

Exclusion criteria:

Patients who will meet one of the following criteria are to be excluded from the study:

Signs of acute heart failure, unstable angina or severe • arrhythmia three months prior to enrolment in the study.

Pacemakers. •

Chronic obstructive pulmonary disease.

Other disorders counteracting exercise testing conditions • that limit lower limb mobility (for example, burns, fractures)

Pre-existing neuromuscular diseases (for example • Myasthenia Gravis).

Patients will be assigned into two groups with a group A receiving HIIT and group B receiving MICT, both groups will receive their optimal medical treatment.

All patients will be thoroughly evaluated before and • after treatment protocol application.

All patients will receive their prescribed medical • treatment.

Evaluation

Primary outcome to be measured is soluble ST2 biomarker level **Secondary out come** to be measured is ejection fraction, quality of life and peak exercise response.

Soluble ST2 biomarker

.1

The Presage(®) ST2 Assay

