(Critical Diagnostics, CA, USA) is an in vitro diagnostic device that quantitatively measures soluble suppression of tumorigenicity 2 (sST2) in serum and plasma by ELISA (Mueller and Dieplinger 2013).

Procedure: sample will be taken at the cubited vein at the beginning of the program and also at its end.

Echocardiogram.

Left ventricular systolic dysfunction will be assessed using the ejection fraction by 2D simpson method (the percentage of the end diastolic volume ejected during systole).

.2

Resting echocardiographic images will be acquired in accordance with American Society of Echocardiography guidelines by a cardiac sonographer, blinded to group allocation *(Lang et al., 2015).*

Procedure: A commercially available ultrasound system (Vivid S5 or E90, GE Medical Systems, Horten, Norway) equipped with a 2.5-MHz multifrequency phased array transducer will be used to determine the echocardiogram variables by the physician.

3. Minnesota Living with Heart Failure Questionnaire

The questionnaire has 21 items. Assessing the impact of frequent physical symptoms of heart failure. Other items ask about the effects of heart failure on physical and social functions as well as mental and emotional functions. Since treatments might have direct effects on a patient's life in addition to their effects on symptoms and functional limitations of heart failure, questions about side effects of medications, hospital stays and costs of care were included to help measure the overall impact of treatments for heart failure on patients' quality of life.

Procedures: When administering the Minnesota Living with Heart Failure Questionnaire to a subject, the instrument must be

completed fully and it is crucial to explain to the patient why it is important to collect his opinions in order to reduce the number of missing data and therefore maximize the quality of the 10 data collected (Appendix II).

4- Modified Bruce exercise test

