A symptom-limited graded treadmill exercise test (GXT) will be carried out prior to the exercise rehabilitation program to tailor the exercise training program using modified Bruce protocol .The following exercise parameters will be assessed: a) Exercise duration, b) estimated achieved metabolic equivalent of task (METs), c) basal heart rate (BHR), d) peak heart rate (PHR) and peak exercise response. The exercise test will be repeated after completion of the 3-month CR program to assess the change in functional capacity of the patients with respect to the fore-mentioned parameters (*Pescatello et al., 2014*).

Procedure:

Exercise will be performed on a treadmill. The leads of the ECG are placed on the chest wall. The treadmill is started at 2.74 km/hr (1.7mph) and at inclinator gradient of 10% after 3 min incline af the treadmill is increased by 2% and the speed increases. The test should be stopped when the subject cannot continue due to fatigue or pain or due to any other medical condition (*Badawy and Muaidi 2019*).

Training

Management procedures

Group A

Patients will receive medical treatment and will be submitted to the cardiac rehabilitation unit receiving HIIT *(pelliccia et al., 2021).*

Frequency: HIIT, MCT will be in 2 supervised sessions per • week for 12 weeks on treadmill.

Intensity: HIIT included 4 minute intervals aiming 60-85% of • heart rate reserve separated by 3 min active recovery period of moderate intensity exercise 40-59% of heart rate reserve.

Duration: The session lasts 30-40 min included warming up • and cooling down at moderate intensity.

Group B

Patient will receive medical treatment and will be submitted to the cardiac rehabilitation program receiving MICT (Mueller et al., 2021).

Frequency: Moderate continuous training is scheduled 2 times • per week for 12 weeks.

Intensity: exercise will be applied on treadmill (40%-59% of • heart rate reserve)

Duration: 30-40 minutes per session.

Safety: all the procedures will be applied inside the cardiac rehabilitation unit.

Only the patients who will complete the 3 month CR program attending $>\!80\%$ of the exercise training sessions will be included in this study.

Data analysis:

The collected data will be statistically analyzed using descriptive statistics (the mean and standard deviation).

The paired t test will be used to determine the significance level • between pre and post physical therapy treatment.

The level of significance < (0.05).

References

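### Does the loosely timed end-of-program blood draw let an acute effect of the last training session into the primary soluble ST2 comparison?

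*Protocol*

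**What the plan says.** Chapter III of the Protocol (Evaluation) names the sST2 level as the primary outcome. The procedure under item 1 states "sample will be taken at the cubited vein at the beginning of the program and also at its end". The only other timing statement that covers sST2 comes just before the Evaluation heading and begins "All patients will be thoroughly evaluated before and"; it goes on to place the second evaluation after the treatment protocol has been applied. Under item 4, the symptom-limited treadmill test is done before the program and again once the three-month program is complete.

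A rest condition is stated for one of the secondary outcomes: "Resting echocardiographic images will be acquired in accordance with American Society of Echocardiography guidelines". None is stated for the blood draw.

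Under Training, the frequency entry begins "HIIT, MCT will be in 2 supervised sessions per"; the unit is the week, and the program runs for 12 of them. The group A intensity entry begins "HIIT included 4 minute intervals aiming 60-85% of", a band expressed relative to heart rate reserve. Between these bouts patients keep exercising for 3 minutes at the band that group B uses throughout. For group B the entry reads "exercise will be applied on treadmill (40%-59% of", on the same scale and without intervals. A closing rule restricts the study to completers with more than 80% attendance and opens with "Only the patients who will complete the 3 month CR program attending".

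**The concern.** The end sample could be taken on the day of the last session, and that session is part of the allocated treatment. Randomisation would not balance an acute effect of it. The Protocol also describes sST2 as a marker that integrates cardiac stress (Chapter II) and says it is thought to be produced in response to injury or stress (introductory background). A harder final bout might therefore leave a higher residue in group A.

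If so, the between-arm contrast in the Hypothesis section would combine a short-lived response with the lasting training effect, and could show a difference that is not there or hide one that is. The paired pre-post t test in Data analysis would be exposed too: a baseline draw taken before training starts follows no session, while the end draw might follow one. Without recorded times, a later analysis could not separate the two effects. The explicit rest condition for echocardiography makes its absence for the primary outcome more noticeable.

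**Working it through.** **No figure in the plan to reproduce.** The Protocol gives 60 patients and a 0.05 significance level, but no effect size, SD or power. The check is a reading of the timing statements, followed by an illustration on assumed values.

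**1. Do the timing statements conflict?** Item 1 puts the draws at the start and end of the program. The general statement puts evaluation before and after treatment. The treadmill test is repeated after completion. All three are consistent with one baseline and one post-program evaluation. What is missing is the detail of that second visit.

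**2. Is a draw on a training day likely?** There are 2 × 12 = 24 sessions, two per week, so five days in seven are not training days. A separate evaluation after the program is already foreseen. A same-day draw is possible but is not what the text points to.

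**3. Is there a documented acute response?** The Protocol's statements on sST2 concern prognosis, severity and suggested tissue sources. None gives a change after a single bout or a time course. Three unshown steps are needed for harm: a draw close to the last session, an acute sST2 response, and a response that differs by arm.

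**4. How large could it be, if it existed?** Assumptions: 30 per arm (no allocation ratio is stated), a two-sided two-sample t test at 0.05 with 58 degrees of freedom, no true training difference, every patient drawn near a session, and a HIIT residue *b* in SDs of the within-patient change. If MICT leaves a share *s* of that residue, the between-arm differential is *d* = *b*(1 − *s*). The noncentrality is *d*·√(30/2) = *d*·√15.

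The documents do not give *s*. Three choices are shown. One takes residue as proportional to mean intensity, using the midpoints of the stated bands over the 4-minute/3-minute cycle:

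- HIIT: (4 × 72.5 + 3 × 49.5)/7 = 438.5/7 = 62.6% of heart rate reserve
- MICT: 49.5%
- *s* = 49.5/62.6 = 0.79, so 1 − *s* = 0.21

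| Assumed *b* (SD) | *s* = 0.79: *d*, error rate | *s* = 0.5: *d*, error rate | *s* = 0: *d*, error rate |
|---|---|---|---|
| 0.1 | 0.021, 5.1% | 0.05, 5.4% | 0.10, 6.7% |
| 0.3 | 0.063, 5.7% | 0.15, 8.8% | 0.30, 20.8% |
| 0.5 | 0.105, 6.8% | 0.25, 15.9% | 0.50, 47.8% |

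The error rate doubles to 10% at *d* of about 0.171 SD. With *b* = 0, or an equal residue in both arms, it stays at 5%. If only half the patients were drawn near a session and *s* = 0.5, the rates are 5.1%, 5.9% and 7.6%.

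For power, take a true difference of 0.736 SD, which 30 per arm detects with 80% power. An opposing differential of 0.05, 0.15 or 0.25 SD lowers power to 74%, 61% or 46%.

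**5. The paired test.** With *n* = 30 and noncentrality *b*√30, an acute shift of 0.1, 0.2 or 0.3 SD present only at the end draw gives a false-positive rate of about 8%, 19% or 36%.

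The outcome depends almost wholly on *b* and *s*, and the Protocol supplies neither.

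**The case for a change.** The strongest case for acting is that sampling conditions belong in a protocol, that an analysis plan cannot repair them once blood is drawn, and that a few sentences would settle the matter at the cost of at most one extra attendance. It is correct that no statement closes the gap, that the acute stimulus differs by arm, and that the paired test would be shifted even by a residue equal in both arms. It is also fair that recording the times of the draw and the last session would be inexpensive.

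These points show that more detail could be written down, not that the plan as written gives a worse answer. A tighter rule would have limits as well. Without a time course, no required rest interval can be derived, so a draw on a non-training day reduces same-day carry-over without guaranteeing its removal. A window anchored on the scheduled end has its own side effect. More than 80% of 24 sessions is more than 19.2, so at least 20 attended and up to 4 missed. If those are the last four, the gap since the last session lengthens by up to two weeks, and it could do so unequally between arms.

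The order of draw and treadmill test is also left open. An effect of the test need not be equal across arms, because a symptom-limited test can reach different workloads once training has changed capacity. Again the Protocol documents no response to the test, so this adds a possibility and not a demonstrated bias.

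**Conclusion.** No change to the plan is called for. The sampling sentence is short on operational detail, but it agrees with the rest of Chapter III, and the natural reading is a draw at the post-program evaluation. A site team would normally settle rest, order and visit day when arranging that evaluation.

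The possible bias has no size that the documents support. The illustrative two-arm error rates run from the nominal 5% to 47.8%, the latter only if the HIIT residue is 0.5 SD, MICT leaves none and every patient is drawn near a session. With residue proportional to mean intensity, the rate does not exceed 6.8% for residues up to 0.5 SD. The two-arm figures rest on an assumed 30/30 split and a two-sample t test that the Protocol does not name; the paired figures rest on an assumed 30 pairs and an acute shift of unknown size. If a single bout leaves sST2 unchanged, nothing is lost.

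Data showing a material acute sST2 response lasting to the time of the draw, or evidence that end samples were routinely taken straight after sessions, would change this conclusion. The Protocol contains neither.

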Aerobic exercises can be continuous, of moderate intensity or intercalating high and low-intensity efforts. High-intensity interval training (HIIT) is currently one of the most effective methods for improving cardiorespiratory and metabolic function. HIIT involves repeated activities, from short to long ones, of high-intensity exercises combined with periods of active or passive recovery (*Tschakert and Hofmann 2013*).

Moderate-intensity continuous training (MICT) is regarded as a successful approach to CR because of its efficacy and safety. Some studies found that MICT can reduce cardiovascular risk and cardiovascular mortality. MICT entails longer durations of moderate-intensity continuous aerobic activity, maintaining intensity between 60 and 80% (VO2peak or reserve heart rate) (Yue et al.,2022).

Recently reported that HIIT is superior to traditional continuous aerobic training in improving cardiac autonomic function and suggested that the effect verified on post-HIIT autonomic

function was related to improve bar reflex modulation and vagal control (*Kiviniemi et al. 2014*).

Several studies reported exercise-induced Moderate Intensity Continuous Training (MICT) favorable cardiac chambers remodeling in post-infarction and in heart failure (either with reduced or preserved ejection fraction) patients (Mueller et al., 2021).

Statement of the Problem:

Is there a significant difference between high intensity interval training versus moderate intensity continuous training on soluble ST2 biomarkers in chronic heart failure?

The Purpose of the Study:

To determine the effect of high intensity interval training versus moderate intensity continuous training on soluble ST2 biomarkers in chronic heart failure.

Significance of the Study:

A recent study of incident HF conducted between 1998 and 2017 in the United Kingdom (UK), age-adjusted rates of first hospitalizations increased by 28% for both all-cause and HF admissions, and by 42% for non-CV admissions. The risk of HF hospitalization is 1.5 times higher in patients with diabetes compared to controls. AF, a higher body mass index (BMI), and higher glycated haemoglobin (HbA1c), as well as a low estimated glomerular filtration rate (eGFR) are strong predictors of HF hospitalizations (Lawson et al., 2019).

Biomarkers have made a significant contribution to the diagnosis and prognosis of disease. Although strongly associated with

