occlusion in a rat model); they measured soluble ST2 mRNA in lung, kidney, and liver tissue samples obtained at prespecified time-points. The liver and kidneys did not participate in ST2 production during any of the studied periods. Concentrations of sST2 have been implicated in the presence and severity of heart failure with particular value for prognostication. It was reviewed the use of sST2 as a prognostic biomarker in heart failure, including present and future directions in this exciting area (*Bhardwaj and James 2010*)

Much published work has examined and confirmed the beneficial physiological effects of aerobic physical activity or moderate intensity (55%–70% of maximal heart rate (MHR), rate of perceived effort (RPE) of 11–13 on the Borg scale) continuous training, known as MICT. World Health Organization (WHO) recommends a minimum of 150 min per week of aerobic physical activity at moderate continuous intensity to maintain or achieve health *(Wood et al., 2019).*

Exercise of high submaximal intensity performed in intervals of 1 to 4 minutes, also called high-intensity interval training (HIIT), has been tested in a multiple studies on patients with heart failure with reduced ejection fraction, showing that HIIT was superior to moderate continuous training (MCT) in improving exercise capacity, quality of life, endothelial function, and left ventricular diameter and ejection fraction. The results were better than those observed in previous studies and meta-analyses of patients with chronic heart failure. They also prompted discussions of whether HIIT should be included in standard care of patients with chronic heart failure. *Guidelines for rehabilitation in patients with cardiovascular disease (JCS 2014).*

Despite concerns regarding patient adherence, several studies have shown irrefutable advantages of HIT in patients with cardiac failure. It is interesting that HIT protocols, the total exercise volume, and time commitment have been significantly lower compared to moderate-intensity training, and yet its use still shows various positive physiological benefits that are at least comparable with moderate-intensity protocols. It is also important to note that HIT has been shown to be safe, tolerable, and enjoyable for patients with cardiovascular disease, eliminating any major concerns of an increase in adverse effect risk (*Hussain et al., 2016*).

CHAPTER III PATIENTS AND METHODS

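### Do the protocol's differing ranges for moderate exercise leave the HIIT and MICT arms too close in intensity to compare?

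*Protocol*

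**What the plan says.** The protocol's operative instructions stand in Chapter III, under Training, Management procedures.

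- **Group A (HIIT):** "HIIT included 4 minute intervals aiming 60-85% of" heart rate reserve, with recovery described as "heart rate reserve separated by 3 min active recovery period of moderate intensity exercise 40-59% of heart rate reserve". On duration: "The session lasts 30-40 min included warming up" and cooling down at moderate intensity. The number of intervals is not given.
- **Group B (MICT):** "exercise will be applied on treadmill (40%-59% of" heart rate reserve), for "30-40 minutes per session".
- **Both arms:** treadmill, two sessions a week for 12 weeks. Patients count if they complete the programme and attend more than 80% of sessions.

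Two other ranges appear in the background. The introduction, citing a review, describes MICT as "maintaining intensity between 60 and 80% (VO2peak or reserve heart rate"). The literature review in Chapter II summarises published work on aerobic training at "55%–70% of maximal heart rate (MHR), rate of perceived effort (RPE) of 11–13 on the Borg scale) continuous training, known as MICT".

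**The concern.** Modality, frequency, programme length and session length are the same in both arms. Intensity and its interval pattern are therefore the whole planned contrast behind the sST2 comparison. If the label for the comparator carries three meanings, and one of them lies inside the band called high intensity, a reader may doubt that the arms differ as intended.

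Three features of the training section add to that doubt:

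- The bands meet at 59/60%.
- HIIT recovery uses the same 40-59% band as the whole MICT session.
- The only compliance rule is attendance, which says nothing about the intensity reached.

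At stake is the reading of a null result. It could mean that intensity does not affect sST2, or that the two arms trained at much the same intensity.

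**Working it through.** The protocol states no figure for the contrast between arms, so there is nothing to reproduce. The check compares the bands directly and then averages over a session.

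**1. Inputs.** From Chapter III: HIIT work 60-85% HRR (midpoint 72.5), HIIT recovery and MICT both 40-59% HRR (midpoint 49.5), 4 min work to 3 min recovery, sessions of 30-40 min. From the background: 60-80% of VO2peak or HRR, and 55-70% of maximal heart rate. Assumed: the number of intervals, and that all other session time is at 40-59% HRR.

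**2. Background range against the HIIT band.** Overlap of 60-80 with 60-85 is 20/25 = 80%. This is exact only if the introduction's range is read as HRR; the sentence also allows VO2peak.

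**3. The second background range.** Converted by (m × peak - rest)/(peak - rest), with assumed resting rates of 60-80 and peak rates of 120-160 bpm, the top end of 70% of maximal heart rate falls at about 10-52% HRR. For example, rest 60 and peak 160 give (112 - 60)/100 = 52%. On these assumptions it stays below 60% HRR and does not reach the HIIT work band.

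**4. Operative bands, work interval against MICT.**

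| Position in band | HIIT work | MICT | Gap (HRR points) |
|---|---|---|---|
| Both at lower limit | 60 | 40 | 20 |
| Both at midpoint | 72.5 | 49.5 | 23 |
| Both at upper limit | 85 | 59 | 26 |
| HIIT at floor, MICT at ceiling | 60 | 59 | 1 |
| HIIT at ceiling, MICT at floor | 85 | 40 | 45 |

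When both arms sit at the same relative place in their bands, the gap is 20 to 26 points. It shrinks to 1 only if the arms go to opposite ends.

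**5. Whole-session mean.** The formula is (t_high × work + (T - t_high) × moderate)/T.

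- Three intervals in 30 min (12 min high; four in 40 min gives the same 40% share):
  - lower limits: (12 × 60 + 18 × 40)/30 = 48.0
  - midpoints: (12 × 72.5 + 18 × 49.5)/30 = 58.7
  - upper limits: (12 × 85 + 18 × 59)/30 = 69.4
- Midpoint gap to MICT: 58.7 - 49.5 = 9.2 points. The extremes are 48.0 - 59 = -11 and 69.4 - 40 = +29.
- Four intervals in 30 min (16 min work + 9 min recovery = 25 min, leaving 5 for warm-up and cool-down): (16 × 72.5 + 14 × 49.5)/30 = 61.8, a gap of 12.3 points.
- Over 2 to 5 intervals the midpoint mean runs from 54.1 (two in 40 min) to 61.8, so the gap runs from 4.6 to 12.3 points.

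**6. The 4:3 cycle alone.** Midpoint mean: (4 × 72.5 + 3 × 49.5)/7 = 62.6, a gap of 13.1 points. Limits: (4 × 60 + 3 × 40)/7 = 51.4 and (4 × 85 + 3 × 59)/7 = 73.9.

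**The case for a change.** The best argument for a change is that the contrast is loosely held. The permitted bands let a compliant HIIT session average inside the MICT band: at the lower limits it averages 44.0-50.7% HRR for 2 to 5 intervals. Attendance is the only stated check. Achieved intensity that is never recorded cannot be recovered by any later analysis, and one number per supervised session is cheap.

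Part of this stands. The ranges permit the overlap of session means, the background and methods differ, and a table of achieved intensity by arm would help a reader of the result.

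The rest does not carry over to a defect in the plan:

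- The session mean is a poor measure of what separates the arms. The protocol describes HIIT as repeated high-intensity bouts with recovery, and its literature review notes lower total exercise volume than in moderate training. Similar session means can go with a real difference in training, because the interval pattern differs anyway.
- Nothing in the document suggests that HIIT patients will sit at their floor while MICT patients sit at their ceiling.
- Sessions are supervised, and a treadmill test before the programme records basal and peak heart rate so that training can be tailored. The means of setting each patient's HRR target are therefore in place. How heart rate is logged and tabulated is detail that a training manual or analysis plan commonly supplies.

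**Conclusion.** No change to the plan follows. The disagreement lies between cited background and methods, not between two instructions. Chapter III applies one scale and one moderate band throughout, and no intensity counts there as both moderate and high. Bands that adjoin without overlapping are an ordinary way to write categories.

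The contrast in the work intervals is 23 HRR points at midpoints and 20 to 26 when both arms sit at the same place in their bands. Near-identical delivery is a corner case. The session-mean gap of about 9 points (4.6 to 12.3 over the counts tried) rests on an assumed interval count and on all remaining time being at 40-59% HRR. No effect on power can be stated, since the protocol gives no effect size or standard deviation for sST2.

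The introduction, the literature review and the Group B range do differ. The sponsor has to reconcile or explain them as a matter of editing, with the clinical team settling any values. That alters neither what patients receive nor how sST2 is compared. Recording achieved %HRR and reporting it by arm is an optional aid to interpretation; it corrects no stated rule and leaves the sST2 result as it is.

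### Does the unstated number of 4-minute intervals leave the HIIT versus MICT contrast undefined?

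*Protocol*

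**What the plan says.** All of the prescription is in the protocol, Chapter III, Management procedures.

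- **Group A, Intensity:** "HIIT included 4 minute intervals aiming 60-85% of" (the scale being heart rate reserve). The recoveries between the work intervals are active, last 3 min and sit at 40-59% on the same scale; the protocol calls this level moderate.
- **Group A, Duration:** "The session lasts 30-40 min included warming up". The cool-down is counted as well, and the level given is again moderate.
- **Group A, Frequency:** two supervised sessions a week for 12 weeks on a treadmill.
- **Group B, Intensity:** "exercise will be applied on treadmill (40%-59% of" (again on the reserve scale), the same band as the recovery periods in Group A.
- **Group B, Duration:** "Duration: 30-40 minutes per session", also twice a week for 12 weeks. It does not say whether warm-up and cool-down are counted.

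Neither the number of work intervals nor the warm-up and cool-down minutes appear anywhere in the protocol. Two background sections describe moderate continuous training with other ranges: the introduction has "maintaining intensity between 60 and 80% (VO2peak or reserve heart rate" and the literature review has "55%–70% of maximal heart rate".

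**The concern.** The protocol calls 40-59% of heart rate reserve moderate intensity, and that band is the whole Group B prescription. Group A's recoveries carry the same band, and its warm-up and cool-down are also described as moderate. By these labels, only the 4-minute work intervals distinguish the arms in intensity, and their number is the one element of the dose that is not written down.

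Two members of staff could both follow the text and deliver different amounts of high-intensity work. The only adherence rule, attendance at more than 80% of sessions, would not register the difference. A null result on sST2 might then reflect few intervals, and a positive one could not be tied to a stated amount of high-intensity exercise. If Group B's warm-up and cool-down came on top of its 30-40 min, total exercise time would also differ between the arms.

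**Working it through.** The protocol gives no interval count and no total of high-intensity minutes, so there is no stated figure to reproduce. The check is how far the stated elements already restrict the dose.

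**Inputs from the protocol (Management procedures).** Work interval 4 min at 60-85% of heart rate reserve; recovery 3 min at 40-59%; session length T of 30 to 40 min; 2 × 12 = 24 sessions; Group B at 40-59%.

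**Assumptions.** Warm-up plus cool-down total W = 5 to 15 min; recovery occurs only between intervals; band midpoints are 72.5% for work and 49.5% for moderate exercise.

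**Step 1: which counts fit.** With n intervals the block lasts 4n + 3(n − 1) = 7n − 3 min, so T = 7n − 3 + W.

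| n | Block (min) | T with W 5-15, within 30-40 | Work per session (min) | Work over 24 sessions (min) |
|---|---|---|---|---|
| 3 | 18 | 30-33 | 12 | 288 |
| 4 | 25 | 30-40 | 16 | 384 |
| 5 | 32 | 37-40 | 20 | 480 |

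Across the whole session range the ratio is 480/288 = 1.67. Six intervals take 39 min and leave at most 1 min for warm-up and cool-down, so the session length caps the dose.

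**Step 2: the same question at one session length.** Three intervals and five intervals never fit the same T.

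- T = 30-33 min: 3 or 4 intervals, 16/12 = 1.33.
- T = 34-36 min: 4 intervals only.
- T = 37-40 min: 4 or 5 intervals, 20/16 = 1.25.

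The rest of the 1.67 comes from the 30-40 min range, which is stated and applies to both arms.

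**Step 3: the intensity contrast.** With all non-work minutes, and Group B, at the moderate midpoint, the difference in session-mean intensity is (4n/T) × (72.5 − 49.5) = (4n/T) × 23.

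- n = 3, T = 33: 12/33 × 23 = 8.4 points of heart rate reserve.
- n = 5, T = 37: 20/37 × 23 = 12.4 points. The spread over all admissible counts and lengths is 12.4 − 8.4 = 4.0 points.
- One interval more at a fixed T adds 4 × 23/T, which is 3.1 points at 30 min and 2.3 at 40 min.

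**Step 4: compare with the width of the work band.** Hold n = 4, T = 35 and moderate exercise at 49.5%.

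- Work at 60%: 16/35 × 10.5 = 4.8 points.
- Work at 85%: 16/35 × 35.5 = 16.2 points.

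The permitted position within 60-85% therefore moves the contrast by 11.4 points, against 4.0 from the interval count. Stating the count would not fix the contrast.

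**Step 5: sensitivity to W.** Two intervals (an 11 min block) need W = 19 to 29 min. If W may reach 20 min, n = 2 also fits sessions of 30 or 31 min, giving 8 work minutes against 16 for four intervals (2-fold) and, at 30 min, 8/30 × 23 = 6.1 points against 12.3. A single interval with W = 20 fills only 24 min and does not reach 30. The one-interval limit in Step 2 thus depends on W not exceeding 15 min.

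**The case for a change.** The strongest case for a change is that session content belongs in the protocol, since no analysis plan prescribes exercise. The interval count is the defining quantity of the experimental arm, attendance does not detect differences in it, and two or three lines would close the gap at no cost. Group A's duration expressly includes warm-up and cool-down while Group B's is silent, so equal exercise time is not guaranteed on paper.

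Much of this stands. The omissions are real, and a report that did not state the delivered session structure would be hard to reproduce. Three parts do not carry further.

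- **The count as the determinant of the contrast.** Step 4 shows that the width of the work band matters more. That a null result might come from too few intervals can also be said of any count that is written down.
- **Unequal exercise time.** The two duration lines give the same 30-40 min per session, and the plain reading is equal session time. No Group B warm-up is mentioned, so any figure for extra minutes would measure something that the text does not contain.
- **The background ranges.** They are cited descriptions of the literature, one of them on the maximal heart rate scale. They do not define the arms and do not contradict Management procedures.

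The setting also limits drift: patients come from one hospital, sessions are supervised in the cardiac rehabilitation unit, and training is tailored from a baseline exercise test.

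**Conclusion.** This is missing detail, not an error. No stated rule or figure is wrong, and the two intensity bands adjoin without overlapping, so the arms remain distinct whichever count is used. Variation in the count falls within the HIIT programme as delivered; it affects how precisely that programme can be described and does not bias the randomised comparison with MICT.

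If warm-up plus cool-down total 5 to 15 min, the open part is one interval at most at a given session length (a ratio of 1.33 or less, 2.3 to 3.1 points of heart rate reserve at band midpoints). It would be larger only with a longer warm-up and cool-down. Writing the count into the protocol would record a value that the investigator has to choose anyway; it would not improve the design or the analysis. The session structure used in each arm, with session time counted the same way in both, can be described when the results are reported. No interval count, duration or intensity is suggested here, and no change to the plan follows.
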